8.3.3 Analysis of Secondary Endpoints

PPVs on a per-patient and per-region-basis of ^{68}Ga -PSMA-11 PET for detection of tumor location confirmed by histopathology/biopsy and conventional imaging follow-up will be calculated and reported along with the corresponding two-sided 95% confidence intervals. The paired McNemar's test will be used to compare the PPVs of ^{68}Ga -PSMA-11 PET imaging to the PPVs of conventional imaging.

Sensitivity, specificity, and NPVs on a per-patient basis of ^{68}Ga -PSMA-11 PET for detection of tumor location confirmed by histopathology/biopsy will be summarized in tabular format. Furthermore, the positive and negative likelihood ratios (LR+ and LR-) will be calculated and reported. Ninety-five confidence intervals of sensitivity, specificity, and NPV will be calculated using the Wilson score method. The comparisons of sensitivity, specificity, and NPV on a per-patient basis of ^{68}Ga -PSMA-11 PET imaging will be compared to of sensitivity, specificity, and NPV on a per-patient basis of conventional imaging using a paired McNemar's test.

Detection rates on a per-patient basis of ^{68}Ga -PSMA-11 PET stratified by PSA value (0.2 - <0.5, 0.5 - <1.0, 1.0 - <2.0, 2.0 - <5.0, 5.0) will be summarized in tabular format and compared between PSA strata using chi-square analysis. The impact of ^{68}Ga -PSMA-11 PET on clinical management in BCR patients will be evaluated using descriptive statistics.

9 Study Management

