3.3.1 Inclusion Criteria

1. Histopathological proven prostate adenocarcinoma.
2. Rising PSA after definitive therapy with prostatectomy or radiation therapy (external beam or brachytherapy).

- a. Post radical prostatectomy (RP) – AUA recommendation
 - i. PSA greater than 0.2 ng/mL measured more than 6 weeks after RP and,
 - ii. Confirmatory persistent PSA greater than 0.2 ng/mL
- b. Post-radiation therapy –ASTRO-Phoenix consensus definition
 - i. Nadir + greater than or equal to 2 ng/mL rise in PSA
3. Karnofsky performance status of ≥ 50 (or ECOG/WHO equivalent).
4. Age > 18.
5. Ability to understand a written informed consent document, and the willingness to sign it.

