In summary, the proposed target accrual of 1,500 patients (375 with biopsies) will provide adequate power for detecting the anticipated improvement in the PPV for both the per-patient and per-region based ⁶⁸Ga-PSMA-11 PET imaging when compared to conventional imaging. However, a sample size of 107 patients with biopsies in total is sufficient for detecting the anticipated improvement in PPV when evaluating per-patient based positive predictive value.

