8.3.2 Analysis of Primary Endpoints

PPVs on a per-patient and per-region-basis of ⁶⁸Ga-PSMA-11 PET for detection of tumor location confirmed by histopathology/biopsy will be calculated and reported along with the corresponding two-sided 95% confidence intervals. The confidence intervals will be constructed using the Wilson score method.

a) Imaging interpretation ⁶⁸Ga-PSMA-11 PET:

PET images will initially be interpreted by a board certified nuclear medicine physician or a board certified radiologist experienced in reading PET at the time of the imaging study at the institution that the study is being performed. These interpretations will not be used for final evaluation. For the data sets included in the analysis for the Primary Endpoint, imaging data will be anonymized and collected at a central site. PET data will be interpreted by three different readers in a random order at separate reading sessions. ⁶⁸Ga-PSMA PET/CT reading training set and guides will be provided and completion of this training will be required for all central review readers.

Visual interpretation:

Regions of suspected disease will be graded on a two-point scale by each reader (0=Negative or 1= Positive). A region will be judged as positive if at least one lesion in this region is visually positive.

- i) Lymph nodes will be considered positive if the ^{68}Ga -PSMA-11 uptake is focal and greater than blood pool (adjacent or mediastinal blood pool). Pelvic lymph nodes will be subclassified according to their localization as follows: R/L obturator, R/L external iliac, R/L internal iliac and other (total of 7 subgroups).
 - ii) Visceral lesions will be considered positive if the ^{68}Ga -PSMA-11 uptake is focal and greater than physiologic background activity of the involvement organ or anatomic site.
 - iii) Bone lesions will be considered positive if the ^{68}Ga -PSMA-11 uptake is focal and greater than physiologic bone marrow.
 - iv) Prostate bed and prostate lesions will be considered positive if the ^{68}Ga -PSMA-11 uptake is focal and greater than physiologic background activity of the involvement organ or anatomic site.
- b) Follow-up Imaging:

All patients will be followed up 3-12 months with conventional imaging (dedicated CT, MRI and/or bone scan). Interpretation of follow-up imaging will be performed by local read. The follow-up conventional imaging should be the same modality/modalities as the initial staging work-up to allow for reproducible and accurate comparisons.

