^{68}Ga -PSMA-11 PET positive findings will be validated as true or false positive as outlined in more detail below. False negative ^{68}Ga -PSMA-11 PET findings cannot be determined as this would require biopsies of ^{68}Ga -PSMA-11 negative but conventional or functional non- ^{68}Ga -PSMA-11 PET positive imaging lesions. Inclusion of such patients however would be violation of the inclusion criteria.

^{68}Ga -PSMA-11 PET validation based on follow-up imaging:

- i) Lymph nodes will be assessed by change in size. ^{68}Ga -PSMA-11 positive lymph nodes will be considered:
 - (1) True positive:
 - If on follow-up imaging within 3-12 months, lymph nodes seen on CT or MRI decrease by more than 30% (for patients undergoing systemic treatment of focal therapy at this site) or increase by more than 20% in short axis diameter (with a minimum of 3 mm in change in size).
 - If patients with solitary lymph node regions show a decrease of PSA by greater than 50% after targeted treatment (i.e. external beam radiation) and the lymph nodes do not change in size (less than 30% decrease or less than 20% increase in short axis diameter).
 - (2) False positive:

- If on follow-up imaging within 3-12 months, sites of initial⁶⁸Ga-PSMA-11 positive lymph node lesions seen on CT or MRI decrease by more than 30% *without* systemic therapy or focal therapy at this site.
 - If ⁶⁸Ga-PSMA-11 positive lymph node lesions do not meet the criteria for above false positive or true positive findings.
- ii) Visceral lesions (non-lymph node soft tissue or organ) will be assessed by change in size. ⁶⁸Ga-PSMA-11 positive visceral lesions will be considered:
- (1) True positive:
- If on follow-up imaging within 3-12 months, visceral lesions seen on CT or MRI decrease by 30% (for patients undergoing systemic treatment of focal therapy at this site) or increase by 20% in largest diameter.
 - If patients with solitary visceral metastasis show a decrease of PSA by greater than 50% after targeted treatment (i.e. external beam radiation) and lesions do not change in size (less than 30% decrease or 20% increase in largest diameter).
- (2) False positive:
- If on follow-up imaging within 3-12 months, sites of initial⁶⁸Ga-PSMA-11 positive lymph node lesions seen on CT or MRI decrease by more than 30% *without* systemic therapy or focal therapy at this site.
 - If ⁶⁸Ga-PSMA-11 positive lymph node lesions do not meet the criteria for above false positive or true positive findings.

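### Section 8.3.3 compares the PPVs and NPVs of PET and conventional imaging with McNemar's test, which does not test predictive values

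*Combined protocol and SAP*

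**What the plan says.** Section 8.3.3 plans two comparisons with conventional imaging. For PPV, per patient and per region: "The paired McNemar's test will be used to compare the PPVs of" PET and conventional imaging. For sensitivity, specificity and NPV, the PET values are set against the sensitivity, specificity and "NPV on a per-patient basis of conventional imaging using a paired McNemar's test". The section does not say which pairs enter the 2x2 table, and no other section does. Section 8.3.2 gives one-sample Wilson intervals for PET, and Section 8.2.1 sizes a one-sample test of PPV against 50%.

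On the reference standard, Section 8.3.2 says that "PET positive findings will be validated as true or false positive as outlined in more detail below", and the rules that follow classify PET-positive lesions only. On false negatives it says that such "PET findings cannot be determined as this would require biopsies of" lesions that are PSMA-negative but positive on other imaging. Its rules for bone count a PET-positive lesion as true if baseline CT, MRI or bone scan shows it. It also states "All patients will be followed up 3-12 months with conventional imaging". Section 3.4, however, sets follow-up at one day, and the schedule in Section 6.1 lists no baseline or follow-up conventional imaging.

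**The concern.** McNemar's test compares two proportions measured on the same subjects. Sensitivity qualifies, because both modalities are scored on all diseased patients. Specificity qualifies on all non-diseased patients. PPV does not: its denominators are the PET-positives and the conventional-positives, which are different and only partly overlapping sets. NPV has the same problem among the negatives.

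An analyst following Section 8.3.3 has to choose a pairing, and each choice tests something other than predictive value. The trial expects PET to detect more disease than conventional imaging. A gain in detection alone could therefore appear in the report as a gain in PPV. Section 1.1 intends the data to be pooled for a marketing application, so a mislabelled comparative claim would matter.

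**Working it through.** **1. The plan's own figure.** The McNemar comparison has no stated sample size or power. The only sizing is the one-sample test in Section 8.2.1 (50% vs 70%, one-sided 0.01, 90% power):

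n = [(2.326 × 0.500 + 1.282 × 0.458) / 0.20]² = 76.6, against a stated 75.

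This agrees closely and does not depend on the point made here.

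**2. What each pairing tests**, with one disease status per patient or region:

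| Pairs used | Quantity tested |
|---|---|
| True positive yes/no, among diseased | sensitivity |
| True negative yes/no, among non-diseased | specificity |
| Positive/negative, all | positivity rate |
| Correct/incorrect, all | accuracy |
| Correct/incorrect, positive on both | no discordant pairs |

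If truth is matched by lesion location, a unit positive on both modalities can be right for one and wrong for the other. Discordant pairs then exist in the last row, but they cover only that subset and do not compare the two PPVs.

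**3. A worked example with equal PPVs.** Assumed: 375 fully verified units, sensitivities 80% and 40%, both PPVs 70%, tests independent given disease. Prevalence is 30%, the prostate-bed figure in Section 8.2.1.

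- False positive rate = prev × sens × (1 − PPV) / [PPV × (1 − prev)]. PET: 0.30 × 0.80 × 0.30 / (0.70 × 0.70) = 0.147. Conventional: 0.073.
- Diseased 112.5: true positives 90 (PET) and 45 (conventional). Non-diseased 262.5: false positives 38.6 and 19.3.
- PPV: 90/128.6 = 70% and 45/64.3 = 70%. There is no difference to find.
- True-positive pairs: PET only 112.5 × 0.8 × 0.6 = 54; conventional only 112.5 × 0.2 × 0.4 = 9. McNemar = (54 − 9)²/63 = 32.1.
- Correct/incorrect pairs: the false-positive discordances are 35.7 (PET only) and 16.5 (conventional only). PET alone correct 54 + 16.5 = 70.5; conventional alone correct 9 + 35.7 = 44.7. McNemar = 5.7.

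Both statistics exceed 3.84 although the PPVs are equal.

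**4. Rejection rates at equal PPVs of 70%.** 20,000 simulated trials per setting, n = 375, two-sided 5%, prevalence 15-50% (Section 8.2.1 gives 15-35% by region; 50% is an assumed per-patient value):

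| Sensitivities (assumed) | True-positive pairs | Correct/incorrect pairs |
|---|---|---|
| 80 vs 40% | 99-100% | 38-90% |
| 70 vs 60% | 20-53% | 7-13% |

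The weighted generalized score test for paired predictive values stayed at 4.7-5.3%, and GEE with robust variance at 4.4-5.2%.

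**5. Missing a real difference.** With PPVs of 70 vs 50% at equal sensitivity (n = 375, prevalence 15-35%), McNemar on true-positive pairs rejects in about 5%; the score test rejects in 62-100%. McNemar on accuracy can also miss. Take an assumed table with PPVs 70/100 (PET) and 45/50 (conventional), in which each modality alone is correct in 32 patients. McNemar is then (32 − 32)²/64 = 0, while the score statistic is 10.6 (p = 0.001).

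**6. NPV.** Assumed table of 380 patients, NPV 40/100 for PET and 80/200 for conventional, both 40%. Among the non-diseased, the discordant pairs are 50 and 10. McNemar = (50 − 10)²/60 = 26.7, p = 2 × 10⁻⁷. The score test gives p = 1.0.

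**7. Verification.** Suppose that only PET-positives have a known disease status. In the example of step 3, the verified conventional positives are 112.5 × 0.8 × 0.4 = 36 true and 262.5 × 0.147 × 0.073 = 2.8 false. The apparent conventional PPV is 36/38.8 = 93%, although the true value is 70%. Across the independent settings it is 85-97%, and even the score test then rejects equal PPVs in 90-99.9%. With latent correlation 0.5 between the tests the figures are 77-88% and 44-94%. Changing the test is therefore not enough without a suitable reference.

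**The case against.** The best defence is that this is an unpowered secondary comparison that no objective or listed endpoint names, and that McNemar would often reach the right answer. Section 8.2.1 expects a PPV of at least 70% for PET against 30-60% for conventional imaging. At 70 vs 50% with the assumed sensitivities above (prevalence 15-35%, n = 375), McNemar on correct/incorrect pairs rejects in 76-99.9% and the score test in 69-99%. That limits the practical harm. It does not make the test valid: the agreement depends on the true values, which the comparison is meant to establish.

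Further limits stand:

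- The sensitivities are assumptions, and the 375 in Section 8.2.1 counts biopsies, not a cohort verified regardless of PET result. The rates above should not be read as this trial's false-positive rates.
- A reader might infer that both-positive patients can never be discordant. That requires one disease status per unit. The endpoint concerns tumor location, so location-matched truth is possible.
- A reader might infer that McNemar is wrong throughout Section 8.3.3. It is the right form for sensitivity and specificity where a reference exists.
- A reader might take "PET imaging when compared to conventional imaging" in Section 8.2.1 as a claim of power for this comparison. It can equally mean the 30-60% benchmark given there, so nothing here rests on it.
- Section 8.3.2 says of PET-negative, conventional-positive patients: "Inclusion of such patients however would be violation of the inclusion criteria". Section 3.3.1 asks for histology and "Rising PSA after definitive therapy with prostatectomy or radiation therapy" but for no imaging finding, and Section 3.3.2 excludes none. This is a separate inconsistency to be reconciled.

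**Conclusion.** The point holds for PPV and NPV. Section 8.3.3 names a test that does not address the stated comparison, and no other section corrects it. The mismatch of denominators needs no numerical assumption. The size of the error does: the documents give no paired accuracy data, so the rates are illustrations under full verification by an independent reference, and the size in this trial is unknown. The error can go either way, as false rejection or as a missed difference, depending on the pairing.

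A reader might infer that the main result or the sample size is compromised. The documents do not support that: the primary analysis is a one-sample PPV with Wilson intervals, and neither the 375 biopsies nor the 1,500 patients depend on McNemar's test. This should be fixed, with high confidence, as a defect in secondary comparisons.

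**What to change.** 1. In Section 8.3.3, keep McNemar for sensitivity and specificity where a reference exists. For PPV, use GEE logistic regression of disease status on test type among positive results, and for NPV among negative results, with independence working correlation and robust variance clustered by patient. This form also allows location-matched truth and pooled regions. The weighted generalized score test is an alternative when each unit has a single disease status.
2. Run the formal PPV and NPV comparison only where disease status is verified regardless of the PET result and independently of conventional imaging. Otherwise report both modalities' PPV and NPV with confidence intervals and no test. As written, Section 8.3.2 classifies only PET-positive findings and builds conventional imaging into the bone reference. The conventional imaging it expects is not scheduled in Sections 3.4 and 6.1, and these sections need to be reconciled.

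The change of test costs two sentences and a few lines of code, with no new data. The second condition may cost more: unless a suitable reference can be defined, the comparative claim becomes descriptive.

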- iii) ⁶⁸Ga-PSMA-11 positive bone lesions will be considered:
- (1) True positive:
- If there was a corresponding positive sclerotic lesion on the CT portion of the ⁶⁸Ga-PSMA-11 PET.
 - If there is focal uptake seen on the baseline bone scan performed within one month of ⁶⁸Ga-PSMA-11 PET.
 - If there is a lesion noted on the initial MRI performed within one month of ⁶⁸Ga-PSMA-11 PET.
 - If within 12 months follow-up CT demonstrates development of sclerosis.
 - If within 12 months follow-up MRI demonstrates a new bone lesion.
 - If within 12 months follow-up bone scan demonstrates new focal uptake.
- (2) False positive:
- If ⁶⁸Ga-PSMA-11 positive bone lesions do not meet the criteria for true positive findings.
- iv) ⁶⁸Ga-PSMA-11 positive prostate bed and prostate lesions will be considered:

(1) True positive:

- If on follow-up imaging within 12 months, lesions seen on CT or MRI decrease by 30% (for patients undergoing systemic treatment of focal therapy at this site) or increase by 20% in largest diameter..
- If patients with prostate bed lesions show a decrease of PSA by greater than 50% after targeted treatment (i.e. external beam radiation) and lesions do not change in size (less than 30% decrease or 20% increase in largest diameter).

(2) False positive:

- If on follow-up imaging within 3-12 months, sites of initial⁶⁸Ga-PSMA-11 positive lymph node lesions seen on CT or MRI decrease by more than 30% *without* systemic therapy or focal therapy at this site.
- If ⁶⁸Ga-PSMA-11 positive lymph node lesions do not meet the criteria for above false positive or true positive findings.

c) Histopathology/Biopsy:

- i) Localization of lesions for histopathology/biopsy will be classified according to the regions in table 1.
- ii) ⁶⁸Ga-PSMA-11 positive findings are aimed to be confirmed by histopathology/biopsy if clinically feasible.
- iii) Histopathological procedures and biopsies will be performed as clinically indicated and as per institutional protocol.

(1) Positive HP/Biopsy: Confirmed sites of metastatic or tumor involvement by histopathology/biopsy will be discussed with the responsible physician/surgeon.

(2) Negative Biopsy: Patients with suspected tumor recurrence on ⁶⁸Ga-PSMA-11 PET with negative histopathology/biopsy will be handled as outlined below:

(a) Lymph nodes:

- For patients undergoing nodal dissection: Patients will be rescanned with dedicated CT or MRI to determine if the suspicious ⁶⁸Ga-PSMA-11 positive node was removed.

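### The planned PPV comparison of PET with conventional imaging is not valid as written: conventional-only findings get no verdict, and in bone the comparator helps define the truth

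*Combined protocol and SAP*

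**What the plan says.** - **Comparison (8.3.3).** "The paired McNemar's test will be used to compare the PPVs of" gallium-68 "PSMA-11 PET imaging to the PPVs of conventional imaging". The reference standard is the composite one: PET PPVs "confirmed by histopathology/biopsy and conventional imaging follow-up will be calculated and reported".
- **Which findings get a verdict (8.3.2 b).** The rules are introduced with "PET positive findings will be validated as true or false positive as outlined in more detail below". Each rule for nodes, visceral lesions, bone and prostate bed then starts from a PSMA-positive lesion.
- **Conventional-positive, PET-negative lesions (8.3.2 b).** The plan says that resolving these would need biopsies, and adds: "Inclusion of such patients however would be violation of the inclusion criteria".
- **Biopsy (8.3.2 c).** It is directed at PET findings: PSMA-11 "positive findings are aimed to be confirmed by histopathology/biopsy if clinically feasible".
- **Bone truth rule (8.3.2 b iii).** One sufficient condition for a true positive reads "If there is focal uptake seen on the baseline bone scan performed within one month of" the PET. A lesion on an MRI within one month is another, and sclerosis on the PET's own CT is a third. The follow-up conditions are developing sclerosis on CT, a new lesion on MRI, or new uptake on bone scan. A PET-positive bone lesion meeting none of these is a false positive.
- **Follow-up (8.3.2 b).** "All patients will be followed up 3-12 months with conventional imaging (dedicated CT, MRI and/or bone scan"), read locally.
- **Expected comparator PPV (8.2.1).** 30-60%.

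**The concern.** A PPV needs a true or false verdict for every positive call of the test in question. The plan supplies this for PET. For conventional imaging it supplies verdicts only where PET happens to be positive too. It does not define a positive conventional scan, and it does not say how a conventional-only finding enters the comparison.

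In bone there is a second problem. The comparator's baseline result is one of the criteria for truth, so bone scan and MRI are partly judged against themselves.

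At stake is the plan's only direct test of PET PPV against conventional PPV. Section 8.2.1 describes the expected gain as an improvement over conventional imaging, and section 1.1 foresees pooling the data for an NDA. As written, the result would depend on the classification rules and on an unstated handling choice as well as on disease. Changing the paired test would not cure this, because any test would use the same comparator verdicts.

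**Working it through.** **1. The plan's own figure.** There is no sample size or power for this comparison. The nearest figure is the 75 in 8.2.1, for PET PPV of 70% against a fixed 50% at one-sided 0.01 with 90% power. The normal approximation gives n = [2.326 × √(0.5 × 0.5) + 1.282 × √(0.7 × 0.3)]² / 0.2² = 76.6, so 77, and 89.3% power at n = 75. That reproduces the figure closely, but it involves no conventional PPV.

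**2. Who gets a verdict under 8.3.2.**

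| | PET positive | PET negative |
|---|---|---|
| Conventional positive | verdict | no rule |
| Conventional negative | verdict | not needed for either PPV |

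PET's PPV uses the first column, which is complete. The conventional PPV uses the first row, and half of that row has no rule.

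**3. Bone.** Take a lesion positive on PET and on a bone scan or MRI within one month. It meets a sufficient condition for true positive whatever its nature. Among bone lesions with an imaging verdict, every bone-scan or MRI positive is therefore true: PPV = 100% before pathology exceptions, against the anticipated 30-60%.

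PET gains from the same rule. If its true bone PPV is t and a share q of its false lesions also shows on baseline bone scan or MRI, the observed PPV is t + (1 − t)q. This assumes that every truly malignant lesion is confirmed by some rule. With t = 70% (the plan's hypothesis) and q = 0-30% (assumed), the result runs from 70% to 0.70 + 0.30 × 0.30 = 79%.

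**4. Other regions, unverified findings dropped.** Let v be the true conventional PPV. Let a and b be the shares of conventional true and false positives that are also PET-positive. Then

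apparent PPV = v·a / [v·a + (1 − v)·b].

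It exceeds v if a > b, equals v if a = b, and is below v if a < b. The documents give neither a nor b, so all values below are assumptions.

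With a = 100% and b = 1 − u:

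| True PPV | u = 25% | u = 50% | u = 75% |
|---|---|---|---|
| 30% | 36% | 46% | 63% |
| 45% | 52% | 62% | 77% |
| 60% | 67% | 75% | 86% |

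For example, 45 / (45 + 55 × 0.75) = 52%.

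- With v = 30%, a = 70-90% and b = 10-30%, the apparent PPV is 50-79%. With b = 50% it is 38-44%.
- With a = b, a true 45% stays at 45%.
- With 30% of true and 25% of false positives dropped: 45 × 0.70 / (45 × 0.70 + 55 × 0.75) = 31.5 / 72.75 = 43%.

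**5. Unverified findings counted as false positives.**

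- Outside bone the apparent PPV becomes v·a. For v = 45% and a = 70-90% that is 31.5-40.5%, below the truth.
- In bone, where double-positive lesions are true by rule, it becomes v·a + (1 − v)·b. This runs from 0.3 × 0.7 + 0.7 × 0.1 = 28% to 0.6 × 0.9 + 0.4 × 0.5 = 74%, so it can lie on either side of the true 30-60%.

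**The case against.** A reader might go further and infer that the conventional PPV is inflated in every region and that PET can therefore never exceed it. The documents do not support that, for these reasons:

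- Nodes, visceral lesions and prostate bed are judged by size change on follow-up or by PSA response, not by baseline conventional positivity. Inflation by rule is confined to bone.
- Elsewhere the bias depends on drop-out shares and on a handling choice that the plan does not state. It can be upward, zero or downward.
- Even in bone, pathology showing another PSMA-positive diagnosis makes the lesion a false positive (8.3.2 c). The baseline rules cover bone scan and MRI within one month, not a dedicated baseline CT. The PPVs are per patient and per region, so the lesion-level 100% need not carry over exactly.
- The bone rules also favour PET, so the net effect on the difference is not one-sided.

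All of this stands. It limits the claim about direction, but it does not make the comparison valid.

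The authors could also answer that they knowingly restricted verification to PET-positive findings and regard the other patients as outside the inclusion criteria. That does not help. Sections 3.3.1 and 3.3.2 contain no criterion on baseline imaging, so such patients can be enrolled. The restriction is also workable for PET's PPV but leaves the comparator's without a complete denominator.

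Finally, deleting the baseline bone rules alone would not be enough. A lesion already visible on bone scan or MRI cannot later appear as new on that modality, and the residual rule would then call it false, pushing both PPVs down. This is correct, and the fix has to deal with it.

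**Conclusion.** The PPV comparison in 8.3.3 is not valid as written. The comparator PPV is undefined overall, because conventional-positive, PET-negative findings have no verdict rule. Among bone lesions with an imaging verdict, the PPV of bone scan or MRI is close to 100% by rule, apart from lesions overturned by pathology. Bone is also the largest expected region, at 35% (8.2.1). These two statements follow from the text without numerical assumptions.

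The size outside bone does rest on assumptions. If unverified findings are dropped and PET is informative, the comparator is overstated, for example 52-77% for a true 45%. With equal drop-out there is no bias, and counting unverified findings as false can put the comparator below the truth. A general claim of inflation would go beyond the documents.

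The consequence is limited to a secondary comparison. The primary biopsy-based analysis of PET PPV against 50% does not use the conventional PPV and is unaffected. The change should be made, but the trial's main conclusion does not depend on it.

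**What to change.** For this comparison only, choose one of two routes in 8.3.3.

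**(a) One reference standard for both modalities.**

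- Classify every region positive on either modality at baseline, by histology or by change on the follow-up imaging already required.
- Do not count baseline bone scan, baseline MRI or the PET's own CT as confirmation.
- Define a positive baseline conventional scan.
- Define what change on follow-up confirms a bone lesion already visible at baseline, since the present criteria of newness cannot apply to it.
- Treat lesions that cannot be resolved as unclassified, not as false positive by default. Report their number, and give both PPVs with all of them counted as true and then all as false.

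**(b) No comparison.** If conventional-positive, PET-negative lesions will not be classified, delete the PPV comparison with conventional imaging and report PET PPV alone.

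**Cost.** Route (a) needs SAP wording and extra classification of lesions, with no new procedure or reader. The schedule in 6.1 lists no baseline conventional scan, so it can cover only patients who have one from their initial work-up. Because biopsy is directed at PET-positive findings, conventional-only findings will rest mostly on follow-up imaging, and this should be stated. Some bone lesions will become unclassified in this comparison. Route (b) costs one secondary comparison. Neither route changes the primary analysis.
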